12. EXTERNAL MONITORING PLAN FOR PUMA STUDY- QUALITY ASSURANCE AND

- 1322 **QUALITY CONTROL**
- 1323 The International Clinical Research Center (ICRC) at the University of Washington will provide
- regular study monitoring for the Thika site in the PUMA study. The Study Monitor will be a Senior
- Research Manager at ICRC. The Research Manager will have Masters in Public Health and/or a
- 1326 Certified Clinical Research Associate (CCRA) certification and will be experienced in site
- monitoring activities.
- 1328 **12.1. Goals and Objectives:** Monitoring is necessary to assure adequate protection of the rights
- of human subjects and the safety of all participants involved in clinical investigations and the
- quality and integrity of the resulting data submitted.
- 1331 The objectives of the monitoring procedures are:
- To ensure that the study is carried out in accordance with the approved protocol
- To identify any problems and suggest / seek solutions

1334 **12.2. Clinical Monitoring Activities**

- 1335 The ICRC Study Monitor will conduct on-site monitoring visits twice annually over the course of
- the 24-month study (12 months of enrollment and 12 months of follow-up). Monitoring visits will
- start no more than 3-months after study initiation.

- The Study Monitor will review standard operating procedures (SOPs) and other study-related documentation on-site and will conduct an in-depth review of a subset of enrolled participants' records. Through this detailed review, monitoring will focus on the following key processes of the study:
- Informed consent process
 - Study eligibility criteria met for all participants
- Timely completion of study CRFs
- Sample collection and handling in accordance to Protocol and SOP(s)
- Review of data management procedure
- Reporting of adverse events and protocols violations according to SOP(s)
- Follow up assessments and procedures
- Product accountability
- Regulatory documents on file

1351

1352

1343

12.3. Clinical Monitoring Report

- The Study Monitor will submit a written monitoring report to the study PI, the site PIs, the co-I and the Thika research team no more than 14 days after the monitoring visit. In this report, the Study Monitor will assess the following items:
- Regulatory review
- 1357 Records review
- Site Operations Assessment
- Status of previous findings
- 1360 Action items

1361

This report will be reviewed in detail with the Thika Research Team at the end of the Monitoring Visit. The Study Monitor will request a written response to any identified "Action Items" within 14 days of the report being submitted, which will include how the team responded to any of the Action Items.

13661367

13. RESOURCE SHARING & DISSEMINATION PLAN

1368 13.1. Resource Sharing:

For all data generated during the course of this project, we will follow the prevailing standards and guidelines in documenting and depositing data sets. We will make quality-controlled raw data as well as processed data used in publications available. As described in the grant application, protocols and workflows will be implemented exactly as described and documented such that other groups will be able to precisely reproduce results from the raw data.

The study personnel assigned to the project, including KEMRI-based, UCSF-based and University of Washington-based investigators, will disseminate results from this research through presentations at public lectures, scientific institutions and meetings, and/or publication in major journals. The institutions and Principal Investigators will adhere to the NIH Grants Policy on Sharing of Unique Research Resources including the Sharing of Biomedical Research Resources: Guidelines for Recipients of NIH Grants and Contracts on Obtaining and Disseminating Biomedical Research Resources. Study records may be reviewed by the U.S. Office of Human Research Protections.

13.2. Data Sharing Plan

Intellectual property and data generated under this project will be administered in accordance with NIH policies, including the NIH Data Sharing Policy and Implementation Guidance of March 5, 2003. Materials generated under the project will be disseminated in accordance with KEMRI, UCSF, University of Washington, and NIH policies. Depending on such policies, materials may be transferred to others under the terms of a material transfer agreement. Access to databases and associated software tools generated under the project will be available for educational, research, and non-profit purposes. Such access will be provided using web-based applications, as appropriate. Publication of data shall occur during the project, if appropriate, or at the end of the project, consistent with normal scientific practices. Research data that documents, supports, and validates research findings will be made available after the main findings from the final research data set have been accepted for publication. Such research data will be modified to prevent the disclosure of personal identifiers to remain in compliance with the Protection of Human Subjects guidelines.

13.3. Publications

We will disseminate the results from this research as broadly as possible. Of note, drafts of publications will be shared with our NIH program office and medical officer prior to submission. First, we will publish our results in Open Access journals, if appropriate. Second, we will post author PDFs of our manuscripts on our respective websites in accordance with the copyright rules of the journals. Third, we will practice posting our manuscripts on Internet archives (such as arxiv.org) when possible.

13.4. Presentations

We expect that all the research personnel will attend national conferences periodically and present the results from this research to the scientific community. Because of the multidisciplinary nature of the work, different group members will present at various conferences, such as the Conference on Retrovirus and Opportunistic Infections, International AIDS Society, and Kenyabased conferences, which focus on the appropriate aspects of our research.

The study team for this award is committed to public dissemination of results of clinical trial, to trial participants, local stakeholders in Kenya, the global scientific community, and US, Kenyan, and global policymakers. Dissemination of study results will follow principles of good participatory practice. The clinical trial has now been registered with Clinicaltrials.gov prior to initiation (NCT0393546) and results will be updated there in a timely fashion. Results will be published in conference abstracts and peer-reviewed journals. Study results will be disseminated through presentations to local stakeholders and policymakers in Kenya, including the Ministry of Health.

14. ETHICAL CONSIDERATIONS

The study protocol, consent forms, and project materials have been reviewed and approved by the KEMRI IRB (**Appendix IX**). The FDA has reviewed and approved the urine tenofovir test as qualifying for a Nonsignificant risk (NSR) indication for an investigational device (**Section 3.4** and **Appendix VIII**)

All participants will provide written informed consent before participation in the trial or in qualitative interviews in their preferred language. Participants will be informed the purpose of the study, the procedures to be followed and the risks and benefits of participation. The consents forms will be translated into Swahili and then back-translated to ensure accuracy. Specifically the participants will be informed that this novel study will answer a critical questions on acceptability, performance and barriers of objective PrEP adherence testing in the context of implementation of PrEP.

Collection and analyses of socio-demographic information and biological samples taken for clinical purposes will be covered by ethics approval. Informed consent will be obtained from potential participants to participate in the study and to store blood and hair samples. These biological specimens will be handled by trained staff and labeled with a unique identifier for each participant. The results will be transmitted to the clinics in an electronic format but only accessed by authorized and trained clinic staff. Only key members of the data team will have access to the electronic data, which will be password protected. Once enrolled into the study participants will be able to withdraw at any point. The link between participant names and codes, used for samples and data, will be destroyed five years after the study is completed,

15. PROTOCOL REGISTRATION

Prior to implementation of this protocol, and any subsequent full version amendments, each site must have the protocol and the protocol informed consent form(s) approved, as appropriate, by their local institutional review board (IRB)/ethics committee (EC) and any other applicable regulatory entity (RE). Upon receiving final approval, sites will submit all required protocol registration documents to the DAIDS Protocol Registration Office (DAIDS PRO) at the Regulatory Support Center (RSC). The DAIDS PRO will review the submitted protocol registration packet to ensure that all of the required documents have been received.

Site-specific informed consent forms (ICFs) WILL NOT be reviewed or approved by the DAIDS PRO, and sites will receive an Initial Registration Notification when the DAIDS PRO receives a complete registration packet. Receipt of an Initial Registration Notification indicates successful completion of the protocol registration process. Sites will not receive any additional notifications from the DAIDS PRO for the initial protocol registration. A copy of the Initial Registration Notification should be retained in the site's regulatory files.

Upon receiving final IRB/EC and any other applicable RE approval(s) for an amendment, sites should implement the amendment immediately. Sites are required to submit an amendment registration packet to the DAIDS PRO at the RSC. The DAIDS PRO will review the submitted protocol registration packet to ensure that all the required documents have been received. Site-specific ICF(s) WILL NOT be reviewed and approved by the DAIDS PRO and sites will receive an Amendment Registration Notification when the DAIDS PRO receives a complete registration packet. A copy of the Amendment Registration Notification should be retained in the site's regulatory files.

- 2051 202. Baeten JM, Donnell D, Mugo NR, et al. Single-agent tenofovir versus combination emtricitabine plus tenofovir for pre-exposure prophylaxis for HIV-1 acquisition: an update of data from a randomised, double-blind, phase 3 trial. *Lancet Infect Dis.* 2014;14(11):1055-1064.

2055

2589 2590	Appendix III: QUALITATIVE GUIDE FOR IN-DEPTH INTERVIEWS FOR WOMEN
2591	Qualitative component: Exploring HIV adherence testing experiences among HIV-1 uninfected
2592	women.
2593	
2594	Target group: Participants enrolled in the intervention arm of the PUMA Study at Thika.
2595	
2596	Objectives:
2597	 Learn opinions of HIV-uninfected participants on PrEP adherence testing.
2598	2. Gain an understanding of how participants performed the PrEP adherence testing
2599	including any challenges experienced.
2600	
2601	Approach:
2602	Focus group discussions will consist of HIV-uninfected women not in serodiscordant relationships;
2603	Four focus group discussions of 5-10 participants each will be conducted.
2604	INTERCHICTION
2605	INTRODUCTION
2606	What kinds of DuCD adharance toots are you aware of?
2607 2608	What kinds of PrEP adherence tests are you aware of? Probe:
2609	
2619 2610	Clinic based PrEP adherence testing?How is PrEP adherence testing performed?
2610 2611	How is PrEP adherence testing performed?
2612	Topic 1: Acceptability
2613	What do you think about Urine testing for PrEP drugs? What are the advantages? What
2614	are the disadvantages?
2615	Possible probes:
2616	What would be the advantages or benefits?
2617	What would be the challenges or disadvantages?
2618	Are there any reasons that would make you not perform a test?
2619	 Possible concerns with urine testing for PrEP drugs?
2620	· · · · · · · · · · · · · · · · · · ·

0.604	
2621	Topic 2: Usability
2622	How was your experience with urine drug-level testing?
2623	Possible probes:
2624	 What challenges did you experience in performing urine drug-level testing?
2625	 Have you shared your results with others?
2626	 Have you used the 24 hour helpline?
2627	
2628	Topic 3: PrEP adherence testing preferences
2629	What would you prefer urine drug testing at home or clinic-based testing?
2630	Possible probes:
2631	 What would you prefer, adherence testing at home or clinic based testing? What
2632	are your reasons?
2633	 What are the things that would make you prefer PrEP adherence testing?
2634	 How did you find the every 3 month testing schedule?
2635	
2636	Topic 4: Closing discussion
2637	Possible probes:
2638	 When people test for adherence, what are some ways to help them have better
2639	PrEP adherence?
2640	 Probe about helping via phone calls, packaging inserts that could provide helpful
2641	messages, what kind of preparation should people have before they have
2642	adherence testing to prepare for the results, etc.
2643	 What would make it easier for you or others to perform adherence testing?
2644	 Do you like the test that says yes/no on adherence or would you prefer a test that
2645	gives you an idea of high, moderate or low adherence?
2646	 Any other thoughts or suggestions on adherence testing that you would like to
2647	share?
2648	

Appendix IV: Focus Group Discussion Guide for Clients

Introduction

Discussion leader will introduce herself and the moderator [and anyone else present from the study team] to the group.

Thank you for coming today to participate in this focus group. We have asked you to participate in this discussion because you are currently taking PrEP for the prevention of HIV. We're conducting this focus group to get your input on a point-of-care test that measures a person's adherence to PrEP by measuring the amount of tenofovir found in the person's blood, urine, or saliva. Tenofovir is one of the drugs found in your PrEP. The goal of this focus group is to understand your feelings about this type of test.

We really appreciate you taking the time to talk with us today. The focus group should take about 1 hour. We are going to audio record the conversation in order to capture all the details and summarize them later on. For that reason, please do not use your name, other people's names, or organization names, including clinic names, to ensure we maintain the confidentiality of the focus group. We will also be taking notes during the discussion to use as a reference. After we've transcribed the focus group discussion, we will delete the audio recording. Please remember that participation in the focus group is completely voluntary, and you may decide to not answer any question as you wish, and you can leave at any time.

Please feel free to think out loud and answer questions as honestly as possible. I encourage all of you to participate in the conversation. And remember that there are no right or wrong answers.

Are there any questions before we begin?

Do I have everyone's permission to record this discussion? [If everyone answers yes, turn on audio recorder.]

Does anyone *not* want to participate? If you would like to leave, please do so at this time.

Discussion Guide

- 1. Has your provider ever talked to you about the need to take your PrEP regularly? Do you ever bring it up? How are those conversations?
- 2. What's it like to answer questions about taking PrEP? Do you think your answers are pretty accurate? What are some reasons why you might not tell the truth?
- 3. What are some of the strategies your provider uses in the clinic to monitor or assess your adherence to your PrEP? What are the strengths and weaknesses of the existing strategies?

4. What happens in the clinic when your provider learns that your adherence is less than perfect?

Now, I'd like to give you a little more information about the test that we'll be discussing today. [Project image of test strips onto screen] This is a simple screening test that would measure whether a person has enough tenofovir in their system that would meet the threshold for protection from acquiring HIV. The test would just indicate a positive or negative result, indicating that a person is adherent to their medication or *not* adherent to their medication. The test strips shown on the screen are an example of what the test would look like. They would be used on urine samples, and results would appear within 5 minutes. Does everyone understand how this test would work before we continue?

would work before we continue?
[Ensure the group understands how the test works before moving on.]

5. What are your initial thoughts about a test like this?

6. Would you want to use this test if it were optional and free at your clinic? Would you want it to be part of your care? If yes, how would it fit in with care for you or others on PrEP?

What if your doctor asked you to use it? Some of you had this testing performed and how did you like it or feel about it?

- 7. How would you feel about using this test on your own (for example, in your home or another private location) instead of using it in the clinic with your provider present? Think about the differences between the two in terms of convenience, privacy, client-provider relationship, effects on your mental health, etc. If you were to use this test on your own, under what circumstances would you use it (e.g., when and why would you use it?)?
- 8. Do you think there would be any benefits or negative effects if your doctor tested you for adherence as a part of routine care? If yes, what are they and why?
- 9. Do you think there are some types of clients who might benefit more from this type of test? If yes, what types? Are there some types of clients who might be negatively affected by being tested for adherence? If yes, what types?
- 10. If you're interested in being tested for adherence, how frequently would you want to be tested? Why?
- 11. If you were tested and your results showed that you had low adherence, how would it affect your pill-taking behavior and your relationship with your provider? How do you think it would affect your mental health?
 - [Probe: Think about both the short-term and the long-term effects on your behavior and your relationship.]
- 12. Overall, what are your final thoughts on being tested for adherence?
- 13. Do you like this yes/no test for adherence or would you want a test that tells you if you have had high, medium or low adherence?
 - 14. Do you have any other concerns or thoughts about this test that we have not yet discussed?

2729	Closure
27302731	Discussion leader will close the focus group around 55 to 60 minutes after it began. She will ask
2732 2733	for any further points from the participants that were not discussed.
2734 2735	Finally, the discussion leader will conclude the focus group and thank the participants for their time.

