We have now developed one of the first such antibody-based (immunoassays) for TFV. Our immunoassay is highly specific (100%), sensitive (96%) and provide TFV levels in urine which correlate strongly with LC-MS/MS-measured levels (r=0.95) in a study of volunteers administered

daily TDF/FTC.¹ In a larger study where TDF/FTC was administered to HIV-noninfected volunteers at 2, 4 and 7 doses a week, the assay showed the same excellent performance characteristics and we were able to establish the adherence cut-off (specifically 1500 nanograms/milliliter) for TFV in urine for the POC assay.² This cut-off minimizes misclassification of adherence and the assay has now being translated to a corresponding lateral flow assay⁴ in a strip format (like a urine pregnancy test, **Figure 6**) to use for this pilot trial. The lateral flow assay has high accuracy compared to the laboratory based enzyme-linked immunoassay (ELISA). See the preliminary data section (**Section 3.3**) for more details on the lateral flow assay.^{4,5}

Real-time feedback of pharmacologic adherence metrics during PrEP will likely increase adherence.

In VOICE, at least 50% of women on active drug had undetectable TFV in *all* plasma tested,⁹¹ but over-reported adherence, even at the last study visit where accurate reporting would not affect study participation.⁹³ Further qualitative work to understand non-adherence in VOICE was performed through the Microbicides Trials Network (MTN)-003D study⁹¹ which recruited participants with pharmacokinetic (PK) data consistent with low (0% of plasma samples having detectable TFV), inconsistent, or high adherence for retrospective disclosure of plasma TFV results and subsequent capture of reactions. Women with low adherence first expressed surprise at the PK results, then acknowledged they were true and revealed reasons for non-drug-taking during in-depth interviews. *Women in all three categories stated that real-time monitoring and feedback in future trials would improve adherence.*⁹¹ Women also said self-report would be more honest if presented with objective adherence metrics.⁹⁴

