1) The non-invasive urine assay will be used to detect the absence or presence of tenofovir (the metabolite of TDF) in urine to improve adherence counseling. TDF is used in HIV treatment regimens worldwide and is also the only agent (in combination with emtricitabine) approved for pre-exposure prophylaxis (PrEP) worldwide. The threshold of the assay was designed to distinguish between people who have taken TDF within the prior four days ("adherent") versus those who have not ("non-adherent") taken TDF within the prior four days. Participants who are considered "adherent" by the assay in the intervention arm of PUMA will be informed of the result and continue to receive standard adherence counseling. Participants who are considered "non-adherent" by the assay will receive enhanced adherence counseling with positive messaging (detailed below).

2) The antibody that was developed against tenofovir for this novel assay is highly selective. As above, the assay has been demonstrated to have very high sensitivity and specificity in our recently concluded clinical validation studies against both the gold standard of measuring drug levels, LC-MS/MS, and the laboratory-based method of performing immunoassays (enzyme-linked immunosorbent assay or ELISA). Therefore, this test has a very low rate of false positivity and we have designed it to have a very low false negative rate. In the unlikely situation of false positive results (where the results indicate "adherent" when the participant is not taking their medication), participants will continue to receive standard adherence counseling. In the very unlikely event of false negative results (where the results indicate "non-adherent" when the participant is taking their medication) the participant will receive enhanced adherence counseling (which does not meet the

definition of "significant risk") in the intervention arm of PUMA. Therefore, participant access to standard adherence counseling will not be affected by a false positive result. We do not anticipate any adverse consequences for participants who receive enhanced adherence counseling due to being wrongly classified as non-adherent (a very rare event). The feedback and adherence counseling will be delivered in a supportive non-judgemental manner (**Figure 8** and **Section 5.5**).

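### The focus-group script describes the urine strip as a check for HIV protection, whereas the protocol describes its cut-off only as a marker of recent dosing or adherence

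*Combined protocol and SAP*

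**What the plan says.** Appendix IV scripts an explanation of the strip between items 4 and 5. It says that the strip would "measure whether a person has enough tenofovir in their system that would meet the threshold for protection from acquiring HIV". The next sentence describes a positive or negative result "indicating that a person is adherent to their medication", or that she is not. The facilitator is then instructed: "Ensure the group understands how the test works before moving on". Item 5 follows: "What are your initial thoughts about a test like this".

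The rest of the protocol describes the cut-off differently:

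- Section 3.1: "we were able to establish the adherence cut-off (specifically 1500 nanograms/milliliter) for TFV in urine for the POC assay".
- Section 3.3: the value was modeled on directly observed dosing, to balance specificity for adherence against sensitivity for non-adherence. One test gives a yes/no reading of recent adherence. The Study Summary says the same.
- Section 3.4 (NSR designation): "The threshold of the assay was designed to distinguish between people who have taken TDF within the prior four days", as against those who have not.
- Appendix V (provider guide): the strip shows whether PrEP was taken in the last few days.

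On protection itself, Section 3.1 says that women likely need 6-7 doses a week. The Figure 8 message for a positive strip (Section 5.5) reminds the woman that strong protection needs a daily pill.

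Acceptability is one of three primary outcomes (Section 6.1). The focus groups, held at study exit, are one of its data sources (Section 6.2).

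**The concern.** Recent drug-taking and protection from HIV are different quantities. The protocol keeps them apart and the script joins them. Study staff would tell women at risk of HIV that an investigational strip checks for protection, a property the protocol does not claim for it.

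There is also a measurement question. The focus groups are meant to record reactions to an adherence test. Whether a woman would want the test in her care (item 6), or would use it alone (item 7), could be answered differently if she takes it to be a protection test. The analysis plan for transcripts (Section 6.4) has no step that would separate the two.

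**Working it through.** **What the cut-off was validated against.** Section 3.3 gives counts for the strip against LC-MS/MS at 1500 ng/mL, and they reproduce (exact 95% intervals):

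| Measure | Counts | Result | Section 3.3 |
|---|---|---|---|
| Specificity | 206/213 | 96.7% (93.3 to 98.7) | 97% (93 to 99) |
| Sensitivity | 86/87 | 98.9% (93.8 to 100.0) | 99% (94 to 100) |
| Accuracy | (206 + 86)/300 = 292/300 | 97.3% (94.8 to 98.8) | 97% (95 to 99) |

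The figures are sound, but they measure agreement with a urine concentration. The second validation, against ELISA, does the same. Neither uses HIV acquisition as an outcome.

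**Descriptions side by side.**

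| Place | What the result or cut-off means |
|---|---|
| Study Summary | recent adherence, yes/no |
| Section 3.1 | adherence cut-off |
| Section 3.3 | adherence benchmark; recent adherence, yes/no |
| Section 3.4 | TDF taken in the prior four days, or not |
| Appendix V | PrEP taken in the last days, yes/no |
| Appendix IV, introduction | adherence to PrEP |
| Appendix IV, explanation, disputed sentence | threshold for protection from HIV |
| Appendix IV, explanation, next sentence | adherent or not adherent |

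Only one row names protection.

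**Does recent dosing imply protection on the protocol's own terms?** Section 3.4 asks whether TDF was taken within four days. Section 3.1 puts the adherence that women likely need at 6-7 doses a week. Taking TDF within four days satisfies the first description without showing that the second was reached. Figure 8 agrees: even after a positive strip, protection is tied to the daily pill.

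**Exposure to the sentence.**

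- Groups and women (Section 6.2): 4 × 5 = 20 to 4 × 10 = 40.
- Items after the sentence: 14 − 4 = 10.
- Items naming adherence: 8, 9, 10, 11, 12 and 13, which is 6 of 10. Item 13, for example, asks "Do you like this yes/no test for adherence".
- Items referring only to the test: 5, 6, 7 and 14, which is 4 of 10.
- Items naming protection: 0 of 10.

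These count exposure to the wording. They do not estimate bias.

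**The case against.** **The sentence is surrounded by correct text.** The introduction to Appendix IV presents the test as a measure of adherence, and the sentence after the disputed one says adherent or not adherent. This stands, and it limits the exposure. It does not withdraw the protection claim, because a listener can take the two sentences together to mean that adherent equals protected.

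**The women already know the test.** Acceptability is assessed in the intervention arm, which is tested at months 0, 3, 6, 9 and 12. A woman could hear up to five Figure 8 messages by exit. This largely stands. Some doubt remains whether every attendee was tested: item 6 says that some were, and Section 6.2 mentions stratifying the qualitative sample by arm. The consent pages are not in the copy reviewed, so what else women were told cannot be judged.

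**Drug levels do predict protection.** Section 3.1 says that urine levels reflect plasma levels, and that plasma levels showed PrEP use associated with more than 90% protection in two trials. One cited title links low urine tenofovir to seroconversion. That is a qualitative bridge, and a reader should not infer that the strip has nothing to do with protection. None of this text states a protective urine threshold, which is what the script asserts.

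**No test or decision rule depends on it.** True. The acceptability survey, the in-depth interview guide (Appendix III), the quantitative feasibility measures and the hair outcome do not use the sentence.

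**Conclusion.** The scripted sentence is not supported by the protocol and should be corrected. It affects one sentence in one qualitative strand of the acceptability outcome, for 20-40 women if all 4 groups are held as planned.

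A reader might infer that the acceptability finding is biased, or that women will leave believing a positive strip proves protection. The documents support neither inference. The size and direction of any effect cannot be derived, the surrounding text is correct, and the clinic's own messages tie protection to daily pills. A reader might also infer that a new scripted disclaimer about protection is needed. It is not: removing the phrase reconciles the guide with the protocol, and a disclaimer would add a health message that appears nowhere in the documents.

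The conclusion rests on the text available here and assumes that the removed consent pages do not define a protective urine level.

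**What to change.** Before the exit focus groups, replace the protection phrase in Appendix IV with the protocol's own description: a yes/no urine test of whether TDF was taken recently, worded to agree with Section 3.4. If any group has already been held with the current wording, say so when reporting those transcripts.

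Two separate drafting slips can be corrected at the same time. Neither bears on the point above.

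- The introduction to Appendix IV says that the test measures the amount of tenofovir in "blood, urine, or saliva". The later explanation in the same guide describes a positive/negative test on urine. The two should be reconciled.
- Appendix V gives both a 3-day and a 4-day window for the same result, and Section 3.4 gives four days. These passages should be reconciled.

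The cost is a few reworded lines in two interview guides and notification to the ethics board. It adds no participants, interviews or assays.
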